COVER PAGE

Peri-implant Phenotype, Calprotectin and Mmp-8 Levels in Cases Diagnosed With Periimplant Disease

[name] DDS, PhD¹, [name] DDS, PhD²

¹Bilecik Şeyh Edebali University, Faculty Of Dentistry, Department of Periodontology, Bilecik, Turkey

²Van Yuzuncu Yıl University, Faculty of Dentistry, Department of Periodontology, VAN,

Turkey

Corresponding Author: [name]

Address: Bilecik Şeyh Edebali University, Faculty Of Dentistry, Department of

Periodontology, [name]

E-mail address: [contact] [contact] Office [contact]

[name]

Bilecik Şeyh Edebali University, Faculty Of Dentistry, Department of Periodontology, [name]

E-mail address: [contact] [contact] Office [contact]

[name]

Van Yuzuncu Yıl University, Faculty of Dentistry, Department of Periodontology, VAN,

Turkey

E-mail address: [contact] [contact]

STUDY PROTOCOL AND STATISTICAL ANALYSIS PLAN

Aim of Research: In this study, it was aimed to investigate the effect of peri-implant soft tissue phenotype on the degree of peri-implant disease and its contribution to the results of non-surgical mechanical treatment, accompanied by clinical and biochemical parameters. The research hypothesis is that better clinical outcomes may be achieved in individuals with thicker soft tissue phenotype.

Scientific Basis and Validity of Medical Research:

Over the last two decades, dental implants have been used to replace missing teeth; It has become a widely accepted and applied therapeutic method to support fixed and removable prostheses (1). A dental implant is generally defined as a root form made of titanium that is placed in place of a natural tooth (2).

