Bacterial pathogens (i.e., periodontal pathogens with a similar composition of the oral microbiota that cause chronic periodontitis) represent the primary etiological factor for periimplant diseases. Additionally, an imbalance of individual local inflammatory response and host-parasite interaction is also implicated for the onset of inflammatory peri-implant diseases. Various risk factors (such as poor oral hygiene, smoking, uncontrolled diabetes, genetic characteristics, alcohol consumption and implant surface) play a role in peri-implant tissue destruction. Insufficiency of keratinized mucosa has also been investigated as a possible risk factor for periimplant diseases (8). Phenotype refers to a dimension that may change over time depending on environmental factors and clinical intervention, and may be site-specific. Periodontal phenotype (3-dimensional image of the gingiva) is determined by gingival phenotype (gingival thickness, keratinized tissue width) and bone morphotype (buccal bone thickness) (9). Peri-implant phenotype can be defined as the dimensional, morphological and topographic features that characterize the clinical condition of the tissues surrounding and supporting osseointegrated implants. The peri-implant phenotype encompasses a soft tissue component, including the osseous component characterized by peri-implant keratinized tissue width, mucosal thickness and supracrestal tissue height, and peri-implant bone thickness. This definition applies not only to buccal/facial regions, but also to lingual/palatal peri-implant regions. Like the periodontal phenotype, the peri-implant phenotype is site-specific and may change over time in response to environmental factors (10). Peri-implant mucosa thickness is the horizontal dimension of peri-implant keratinized or non-keratinized soft tissue. Periimplant supracrestal tissue height is the vertical dimension of the soft tissue surrounding a dental implant from the mucosal margin to the crestal bone. Unlike keratinized mucosa width and mucosal thickness, this component of the peri-implant soft tissue phenotype courses circularly around an implant, including proximal regions. Peri-implant bone thickness is the horizontal dimension of the bone tissue supporting the osseotegrated implant. The optimal dimensions of all components of the phenotype to maintain peri-implant tissue health is a controversial issue. However, current studies show that keratinized mucosa, mucosal thickness and periimplant bone thickness are less than 2 mm; confirmed that marginal inflammation is greater in areas where the supracrestal tissue height is less than 3 mm (10). Biomarkers in peri-implant crevice fluid also provide promising results in terms of diagnostic

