The patients to be included in the research will be selected among 50 volunteer individuals aged between 18-65 who applied or were referred to Van Yüzüncü Yıl University Faculty of Dentistry Department of Periodontics with complaints of inflammation in the peri-implant area and were diagnosed with peri-implantitis disease. People who have systemic diseases, smokers, have used antibiotics or received any other medical treatment within 6 months, and are pregnant or breastfeeding will be excluded from the study. Additionally, individuals who

met the definition of peri-implant health and individuals who required surgical treatment of peri-implantitis were excluded from the study.

The peri-implant soft tissue phenotype of all participants who are detected to have periimplant disease and will be included in the study will be measured, necessary clinical and radiological examinations will be performed, necessary samples will be collected and conventional mechanical treatments will be applied. The data of all participants will be collected again in the 6th month following the treatment.

Patient Data Records, Peri-implant Disease Treatment

The details of the application and the research to be conducted will be explained to the patients who will participate in the study, and an informed consent form will be signed. Patients diagnosed with peri-implant disease will be asked for routine examinations before treatment, intraoral photographs will be taken, and clinical and radiological examinations will be performed in detail. Detailed anamnesis of patients who meet the selection criteria will be taken and clinical and radiological examinations will be performed. Patients with caries on their teeth will be directed to Restorative Dentistry Department and restorations of existing caries will be made at the relevant clinic. Before starting their treatment, patients who meet the selection criteria will be given detailed information about periodontal and peri-implant diseases, microbial dental plaque that causes these diseases, and methods of preventing microbial dental plaque. Individuals will be taught how to brush their teeth, how to use an interdental brush.

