Peri-implant crevice fluid (PIOS) samples will be collected from all individuals before proceeding with mechanical treatment of diseased implant sites. The areas will be isolated from saliva with cotton pellets, dried with light air, and paper strips (PerioPaper®) will be kept in the trough for 30 seconds (13). Paper strips obtained from each implant will be placed in Eppendorf tubes containing isotonic Ph:7.4 phosphate buffer solution and stored at -40 ° C until analyzed in the laboratory department of our clinic. Routine periodontal parameters such as plaque index (PI) (14), gingival index (GI) (14), bleeding on probing and probing pocket depth scores of the patients whose PIOS samples are collected will be recorded with a Williams-type plastic probe. Following these procedures, the patients' peri-implant phenotype will be evaluated. In the evaluation, the traditional transgingival probing technique and a newly developed technique will be used simultaneously and their correlations with each other

will be examined. A digital caliper with a sensitivity of 0.01 mm will be used to measure transgingival probing values to determine peri-implant mucosa thickness. Measurements will be made from two points: apical of the free gingival sulcus and coronal of the mucogingival junction. After the peri-implant mucosa thickness measurement points are determined with a marker pen, Xylocaine® spray (Vemcaine 10%, lidocaine) or, if necessary, local anesthetic (Maxicaine, lidocaine hydrochloride) will be applied to prevent the patient from feeling pain. Measurements will be made from the marked points in a direction perpendicular to the peri-implant mucosa, using a 10-gauge endodontic spreader (G-Star Medical Co., Ltd., Guangdong, China) with a silicone stopper until its contact with the alveolar bone is felt. Since excessive force will cause the spreader to exceed the soft tissue and advance in the alveolar bone, care should be taken to apply only light forces that can be limited to the soft tissue. After all measurements are repeated twice by the same researcher at 10-minute intervals, the amount of peri-implant mucosa thickness in each region will be determined by taking the average of the two measurements.

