Descriptive statistics for the features emphasized will be expressed as Median, Average, Standard Deviation, Minimum and Maximum value. In terms of these characteristics, two-factor and one of the factors repeated-measures analysis of variance will be used to compare group averages and periods (0th month and 6th month). To determine the relationship between variables, Pearson or Spearman correlation coefficients will be calculated separately in the groups. In the calculations, the statistical significance level will be taken as 5% and the SPSS statistical package program will be used for the calculations.

Figure- 1. Clinical Index Form

PLAQUE INDEX

REFERANCES

1 COSGAREA, Raluca; SCULEAN, Anton; SHIBLI, Jamil Avad And SALVI, Giovanni Edoardo. Prevalence Of Peri-İmplant Diseases – A Critical Review On The Current Evidence. Braz. Oral Res. [Online]. 2019, Vol.33, Suppl.1, E063. Epub Sep 30, 2019. ISSN 1807-3107.

5. Caton, J. G., Armitage, G., Berglundh, T., Chapple, I. L. C., Jepsen, S., Kornman, K. S., ... Tonetti, M. S. (2018). A new classification scheme for periodontal and peri-implant diseases and conditions - Introduction and key changes from the 1999 classification. Journal of Clinical Periodontology, 45, S1–S8. doi:10.1111/jcpe.12935

6. NOVAES JUNIOR, Arthur Belém et al. New strategies and developments for periimplant disease. **Braz. oral res.**, São Paulo , v. 33, supl. 1, e071, 2019 . access on 09 June 2020. Epub Sep 30, 2019.

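### Mucosal thickness is classified while sites are inflamed and month 0 is compared with month 6 without baseline adjustment, so a change-based test could favour thick tissue with no true phenotype effect.

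*Combined protocol and SAP*

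**What the plan says.** - **Who is classified.** Under Patient Selection and Study Protocol, participants present with "complaints of inflammation in the peri-implant area", and those who meet the definition of peri-implant health are excluded. The plan then measures "The peri-implant soft tissue phenotype of all participants who are detected to have periimplant disease". No site is classified in a quiet state.
- **When.** Under Patient Data Records, Peri-implant Disease Treatment, the order is fluid sample and clinical indices, then transgingival thickness with a 1 mm cut, then the colour-tipped probe, and only then debridement.
- **Stability of the trait.** The scientific background says: "Phenotype refers to a dimension that may change over time depending on environmental factors and clinical intervention, and may be site-specific".
- **Hypothesis.** The Aim of Research expects that "better clinical outcomes may be achieved in individuals with thicker soft tissue phenotype".
- **Analysis.** The Statistical analysis section plans a two-factor ANOVA with time (months 0 and 6) as the repeated factor. It names no baseline covariate, does not define the groups, and does not say which term of the model tests the hypothesis. It adds that "the statistical significance level will be taken as 5" per cent.
- **Size.** Participants are "selected among 50 volunteer individuals aged between 18-65". No effect size, SD or power is given.

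**The concern.** The grouping variable is read at the same visit, and at the same inflamed site, as the baseline outcome. If swelling adds to the reading, a site that is thin when quiet can cross 1 mm and be classed as thick because it is inflamed. The thick class would then start worse and, by regression to the mean and resolution of swelling, show the larger fall at month 6.

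With two groups and two times, the group-by-time test is identical to a t test on change. That test could therefore appear to confirm the hypothesis with no phenotype effect at all. The same mechanism would make thick sites look more diseased at baseline, which distorts the aim concerning the degree of disease.

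**Working it through.** The plan has no calculation of its own to reproduce. From the documents: 50 participants, a 1 mm cut, a 5% level and times 0 and 6 months. Everything else is assumed.

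**Assumptions.** True thickness T has mean 1.2 mm and SD 0.4 mm. Baseline inflammation I0 and month-6 inflammation I6 each have SD 1 and correlate 0.5. Measured thickness is M = T + b × I0, where b is swelling in mm per SD of inflammation. Phenotype has no effect, and T and I0 are independent.

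**Formulas.**
1. SD of M: s = √(0.16 + b²). Correlation of M with I0: ρ = b/s.
2. Standardised cut: c = (1 − 1.2)/s. Share classed thick: P = Φ(−c).
3. Baseline difference, thick minus thin: D = ρφ(c)/[P(1 − P)].
4. False extra improvement: (1 − 0.5) × D.
5. Variance of change: 1 + 1 − 2(0.5) = 1. So SE = √{1/[50P(1 − P)]}, and k is step 4 divided by SE.
6. Rejection rate ≈ Φ(k − 1.96) + Φ(−k − 1.96).

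**Worked case, b = 0.2.** s = √0.20 = 0.447; ρ = 0.447; c = −0.447; φ(c) = 0.361; P = 0.673. D = 0.447 × 0.361/(0.673 × 0.327) = 0.73. Half of that is 0.37. SE = √[1/(50 × 0.220)] = 0.301; k = 1.22; rejection ≈ 0.23.

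| b (mm per SD) | ρ | P thick | Baseline difference D | False extra improvement: formula / simulation | False-positive rate: formula / simulation |
|---|---|---|---|---|---|
| 0.05 | 0.124 | 0.690 | 0.20 | 0.10 / 0.10 | 6% / 6% |
| 0.1 | 0.243 | 0.686 | 0.40 | 0.20 / 0.21 | 10% / 10% |
| 0.2 | 0.447 | 0.673 | 0.73 | 0.37 / 0.37 | 23% / 23% |
| 0.3 | 0.600 | 0.655 | 0.98 | 0.49 / 0.49 | 38% / 37% |

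**If thin sites are truly more inflamed (correlation 0.3).** The covariance of M and I0 becomes b − 0.3 × 0.4 = b − 0.12, and the variance of M becomes 0.16 + b² − 0.24b. The same steps give a false extra improvement of −0.04, 0.17 and 0.35 SD at 0.1, 0.2 and 0.3 mm. The bias about cancels at 0.1 mm and is smaller, but present, above that.

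**Baseline adjustment.** In this model I6 depends on I0 and not on T, so once I0 is in the model the class carries no further information. Simulated rejection with ANCOVA was about 5% in every setting.

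A second simulation used other assumptions: thickness mean 1.1 mm and SD 0.3 mm, error in both thickness and outcome, and persistence of inflammation from 0 to 0.6. With nonzero swelling and no thin-inflammation link, ANCOVA rejected in 4.8% to 9.8% of trials, against 6.2% to 83.8% for the unadjusted group-by-time test. The residual error ran against thick tissue.

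**The case against.** **The size is unknown, and an opposing link is documented.** This stands. The documents give no swelling figure, thickness SD or persistence of inflammation. At 0.05 mm per SD the false-positive rate is only about 6%. The background section also reports more marginal inflammation where tissue dimensions are small, which works against the bias. An unmeasured offset is not a safeguard, but it rules out saying that the artefact will occur.

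**The bias belongs to change, not to month-6 level.** This also stands. Unadjusted month-6 levels would look equal or worse for thick tissue: at 0.2 mm in the second simulation, 0 to 0.52 SD worse. Because the plan does not say which term tests its hypothesis, the exposure arises only if the group-by-time term is used.

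**A reader might infer that bone loss also inflates the reading**, since the instrument is advanced "until its contact with the alveolar bone is felt" and this disease removes bone. The documents do not say that bone loss raises this horizontal measurement, and it was not modelled. It forms no part of the point.

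**A reader might infer that reclassifying at month 6 solves the problem**, because "The data of all participants will be collected again in the 6th month following the treatment", and that results by the two classes would bracket the truth. They need not. Below, negative values favour thick tissue.
- If month-6 variance falls to 0.40, the bias in change at 0.1, 0.2 and 0.3 mm is −0.20, −0.36 and −0.49 SD by month-0 class, and −0.04, −0.07 and −0.11 SD by month-6 class. Both lie on the same side of zero.
- With the 0.3 thin-inflammation link and 0.1 mm swelling, the biases are +0.04 and +0.45 SD. Again there is no bracket.
- A baseline-adjusted comparison by month-6 class is worse than the problem it is meant to solve. Under the main assumptions its bias is +0.30, +0.57 and +0.77 SD, with 20%, 58% and 87% false positives, because that class is contaminated by month-6 inflammation.

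**Conclusion.** The point holds as a possible bias in change-based comparisons. Three facts are documented: sites are enrolled inflamed, classified before treatment, and analysed without baseline adjustment. That the groups are the phenotype classes is inferred from the aim and hypothesis.

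Under the main assumptions the false-positive rate runs from about 6% at 0.05 mm of swelling per SD to about 37% at 0.3 mm. It is lower, and near nominal at 0.1 mm, if thin sites are truly more inflamed. The documents do not support the stronger reading that a thick-tissue advantage would necessarily be an artefact. They support only that the planned test, read as group by time, could not tell the two apart.

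**What to change.** 1. In the Statistical analysis section, define the groups as the baseline phenotype classes. Make the test of the response hypothesis a comparison of the month-6 outcome between those classes, adjusted for the baseline value of the same outcome (ANCOVA), in place of the unadjusted group-by-time test. This removes most of the artefact, not all of it if the outcome is measured with error.
2. Describe the baseline relation between phenotype and severity as an association, not an effect.
3. Do not repeat the response comparison by month-6 thickness class, and do not present two classifications as a bracket.
4. Reconcile two passages. The background section plans a connective tissue graft where thin biotypes are found, while Patient Selection and Study Protocol describes conventional mechanical treatment for all. A graft would alter the thin group's response and so affect this same comparison.

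Items 1 to 3 cost SAP wording only: the baseline values are already collected, and no visit or participant is added. The downside is that the phenotype difference may come out smaller.

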
and prognostic values. A biomarker is a parameter that is objectively measured and evaluated as an indicator of normal biological, pathogenic processes or responses to therapeutic intervention. The imbalance between bacterial load and host response at the soft tissueimplant interface triggers an inflammatory process. Cytokines such as tumor necrosis factor alpha, Interleukin-1-beta, and Interleukin-6 are produced by dendritic cells, connective tissue fibroblasts, macrophages, and neutrophils, as well as a number of enzymes, such as matrix metalloproteinases, by neutrophils, fibroblasts, and osteoclasts, which promote the synthesis of connective tissue collagen, and causes deterioration of alveolar bone. Such cytokines and enzymes can be detected in peri-implant groove fluid by various tests and allow objective evaluation in determining prognosis (11). Nowadays, periodontal and transgingival probing measurement techniques are frequently used to determine gingival thickness. In our study, peri-implant mucosa phenotype will be measured with a newly developed probe (Hu-Friedy Colorvue Biotip Probe®) with a colored tip that will be placed in the gingival sulcus, and the relationship between peri-implant disease and peri-implant phenotype will be investigated. Additionally, since the method to be applied is different, whether it is a reliable method will be compared with the literature and the conventional method (transgingival probing). In our study, connective tissue graft, one of the soft tissue augmentation methods, will be applied to the areas where thin biotypes are detected as a result of our analysis methods. Recent studies (12) have emphasized that soft tissue augmentation procedures applied in areas with periimplant disease can provide significant reductions in bleeding on probing and gingival index values, and in addition, there may be an increase in marginal bone levels. In the light of all this information, the aim of our study is to investigate the effect of peri-implant soft tissue phenotype on the degree of peri-implant disease and its contribution to the results of nonsurgical mechanical treatment, accompanied by clinical and biochemical parameters.

Study Protocol, Methods and Procedures to be Applied: Patient Selection and Study Protocol

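### Correlation with transgingival probing cannot show that the colour-tip probe is reliable; the method comparison needs an agreement analysis and a stated criterion

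*Combined protocol and SAP*

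**What the plan says.** In the combined protocol and SAP, the section Scientific Basis and Validity of Medical Research says that "peri-implant mucosa phenotype will be measured with a newly developed probe" and then asks "whether it is a reliable method will be compared with the literature and the conventional method (transgingival probing".

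The section Patient Data Records, Peri-implant Disease Treatment gives the comparison: "the traditional transgingival probing technique and a newly developed technique will be used simultaneously and their correlations with each other" will be examined. It describes the two techniques as follows.

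- **Caliper (transgingival probing).** "Measurements will be made from two points: apical of the free gingival sulcus and coronal of the mucogingival junction". The spreader is advanced "until its contact with the alveolar bone is felt". "After all measurements are repeated twice by the same researcher at 10-minute intervals", the two readings are averaged. Below 1 mm is thin and above 1 mm is thick.
- **Colour-tip probe.** Each pocket gets one of four ordered classes (thin, medium, thick, too thick), with no millimetre value. Thin means that the white tip shows through.

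The section Statistical analysis lists descriptive statistics, a repeated-measures analysis of variance, and this on relationships between variables: "Pearson or Spearman correlation coefficients will be calculated separately in the groups". The documents contain no kappa, percent agreement, sensitivity, specificity, repeatability statistic or threshold for calling the probe reliable.

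**The concern.** The practical question is whether a site that one method calls thin is also called thin by the other. Correlation asks something else: whether thicker sites tend to get higher colour classes. If the white tip stops showing at 0.8 mm instead of 1.0 mm, the ranking is nearly preserved and many thin sites are missed. Followed as written, the plan could report a good correlation for a probe that labels too few or too many sites thin.

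Several details of the same comparison are open. Two caliper points face one colour reading, with no matching rule. The order of the readings and any masking are unclear. It is also unclear whether the colour reading is repeated. Finally, the plan does not say which method defines phenotype in the main analysis.

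**Working it through.** **Inputs from the documents.** Caliper cut 1 mm, four ordered colour classes, 50 participants, 5% significance level. There is no stated agreement target or sample size derivation, so there is no figure of the plan's own to reproduce.

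**Assumed inputs.** True thickness T is lognormal with mean/SD 1.5/0.5, 1.2/0.4 or 1.0/0.3 mm. The caliper is error-free. Probe error e is normal with SD 0.2 mm. Colour cut-offs are 1.0/1.4/1.8 mm, all moved by a shift s.

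**Formulas.**
- Caliper thin: T < 1. Probe thin: T + e < 1 + s.
- Sensitivity = P(probe thin | caliper thin). Specificity = P(probe not thin | caliper not thin).
- Kappa = (po - pe)/(1 - pe), where po is observed and pe is chance agreement.
- Spearman is between T and the four-level colour class.

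Check of one input, mean 1.2/SD 0.4: log-variance = ln(1 + 0.4²/1.2²) = 0.105, log-SD 0.325, log-mean = ln 1.2 - 0.053 = 0.130. P(T < 1) = Φ(-0.130/0.325) = Φ(-0.40) = 0.34.

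**Results (simulation).**

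| Mean/SD, mm | Shift, mm | Spearman | Sensitivity | Specificity | Kappa | % thin, probe/caliper |
|---|---|---|---|---|---|---|
| 1.5/0.5 | 0 | 0.87 | 0.74 | 0.93 | 0.61 | 17/14 |
| | -0.2 | 0.85 | 0.40 | 0.99 | 0.49 | 7/14 |
| | +0.2 | 0.87 | 0.94 | 0.79 | 0.48 | 31/14 |
| 1.2/0.4 | 0 | 0.82 | 0.78 | 0.87 | 0.64 | 35/34 |
| | -0.2 | 0.83 | 0.47 | 0.97 | 0.49 | 18/34 |
| | +0.2 | 0.79 | 0.95 | 0.67 | 0.55 | 54/34 |
| 1.0/0.3 | 0 | 0.73 | 0.81 | 0.81 | 0.61 | 53/56 |
| | -0.2 | 0.75 | 0.51 | 0.96 | 0.44 | 30/56 |
| | +0.2 | 0.65 | 0.96 | 0.55 | 0.53 | 73/56 |

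As counts, in the middle scenario with 50 sites: 0.34 × 50 = 17 are thin. The unshifted probe finds 17 × 0.78 ≈ 13. At -0.2 mm it finds 17 × 0.47 ≈ 8, with Spearman slightly higher.

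**Varying the inputs.** Over 27 sets (three thickness scenarios, error SD 0.1-0.3 mm, class width 0.3-0.5 mm):
- -0.2 mm: Spearman changes by -0.05 to +0.04, while sensitivity goes from 0.67-0.90 to 0.33-0.51.
- +0.2 mm: Spearman changes by -0.14 to +0.02, while specificity goes from 0.75-0.96 to 0.52-0.81.

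The result does not depend on the lognormal form. With normal thickness (mean 1.2, SD 0.4), error SD 0.1 and cut-offs 1.0/1.3/1.6 mm, a +0.3 mm shift takes Spearman from 0.93 to 0.85 and kappa from 0.84 to 0.46.

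**At 50 independent sites.** Separation of a shifted from an unshifted probe (AUC; 0.5 = none, 1 = complete), in the order of the three scenarios:

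| Statistic | -0.2 mm | +0.2 mm |
|---|---|---|
| Spearman | 0.64/0.54/0.60 | 0.51/0.66/0.76 |
| Kappa | 0.68/0.81/0.86 | 0.72/0.74/0.70 |
| Paired difference in % thin | 0.94/0.98/0.99 | 0.98/0.99/0.99 |

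The exact McNemar test rejects in 15/72/96% of trials at -0.2 mm and in 81/86/73% at +0.2 mm. The 15% reflects only about 0.14 × 50 = 7 thin sites.

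The smallest correlation significant at two-sided 5% is t/√(48 + t²) with t = 2.01, which is 0.28. A significant coefficient is therefore weak evidence of reliability.

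**Precision.** The 95% half-width for kappa is 1.96 × √(po(1 - po)/50)/(1 - pe). At kappa 0.6 with 30% thin by both methods: pe = 0.58, po = 0.832, half-width = 1.96 × 0.0529/0.42 = 0.25. The simulated half-widths are 0.33/0.23/0.22.

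**If correlation is computed within caliper thin and thick groups.** An unshifted probe has a Spearman of only 0.33-0.36 in thin sites in the base case (about 0.25-0.41 over the 27 sets), through range restriction alone.

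**The case against.** The strongest reply is that the method comparison is an additional question in a 50-patient study, and that every millimetre input above is assumed. Both are true, and they limit the severity. They do not rescue correlation, because its insensitivity to a shift in cut-offs holds across the inputs tried.

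The contrast is also not uniform. At +0.2 mm with mean 1.0 mm, Spearman falls from 0.73 to 0.65 and separates the probes slightly better than kappa (0.76 against 0.70). That stands. It is why kappa should not be the only agreement statistic. Treating the caliper as error-free is a further simplification, since bone contact is judged by feel.

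A reader might infer more than the documents support:

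- **That the group-wise coefficients are the method comparison.** The Statistical analysis sentence is general and may concern clinical and biochemical variables. Applying it here, and taking the groups to be caliper groups, are both inferences.
- **That the colour reader already knows the caliper value.** One sentence has the techniques used simultaneously. Another calls the colour reading the second evaluation, which may mean only the second method. Order and masking are unclear, not settled.
- **That the colour probe is read only once.** The sentence on repeats stands in the caliper description but refers to all measurements.
- **That the main exposure is misclassified.** This would need the colour probe to define phenotype. The background suggests that it does, but the methods also classify by caliper.
- **That the probe is unreliable.** Nothing here shows that; the plan simply could not tell.

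**Conclusion.** The concern holds for the additional question of whether the colour-tip probe is reliable. Correlation is the only statistical comparison planned, no criterion is stated, and the literature comparison has no method. Under the assumed inputs, a shift of half a colour class (0.2 mm against a class width of 0.4 mm) can cut sensitivity for thin sites from 0.74-0.81 to 0.40-0.51 while Spearman moves by about 0.02 or less. In the other direction it can cut specificity from 0.81-0.93 to 0.55-0.79, with Spearman unchanged in one scenario and lower by 0.03 and 0.08 in the other two. Correlation thus reacts partly to some shifts and hardly to others.

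These sizes rest on assumed thickness distributions, colour cut-offs and probe error, and on an error-free caliper. That correlation does not measure agreement needs none of them. The plan should be changed on this point, but the stated aim does not depend on it unless the colour probe defines phenotype, which the documents leave open.

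**What to change.** For the method comparison, replace correlation as the basis for calling the probe reliable with one agreement analysis pooled over all sites:

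1. Cross-tabulate the four colour classes against caliper thickness. Limits of agreement do not apply directly, because the probe gives no millimetre value.
2. For white tip visible against caliper below 1 mm, report sensitivity, specificity, kappa and the paired difference in the proportion called thin (McNemar). How well kappa shows a shift depends on the scenario.
3. Give 95% intervals that allow for several points or implants per patient, for example a bootstrap by patient, or use one prespecified site per patient. The wording "Paper strips obtained from each implant" suggests that a patient may contribute more than one implant.
4. Name in advance the caliper point, or the mean of both, that is matched to the single colour reading. State which results would be called reliable.
5. If the group-wise correlations were meant for this comparison, do not use them for it.
6. Record the subjective colour class before the caliper value is obtained.
7. Report caliper repeatability from the duplicate readings. Clarify whether the repeats cover the colour probe; if they do not, say that its repeatability is not assessed.
8. State which of the two methods defines phenotype in the main analysis.

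The cost is analysis wording and a fixed order for two readings already planned, with no extra patients, visits or measurements. There are two downsides. The caliper reader may then know the colour class, and that reading also needs judgement. With about 50 sites, precision is only moderate (95% half-width for kappa about 0.2-0.3), so results should be reported as estimates with intervals.
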